6.2.5 Definitions of dose limiting toxicities (DLTs)

DLTs are listed in Table 6-3, and will be defined as all AEs of the specified grade occurring within Days 1-28 of the combination phase, unless clearly and incontrovertibly due to extraneous causes.. Table 6-3 was created using Common Terminology Criteria for Adverse Events (CTCAE) v4.03.

For the purpose of dose-escalation decisions, only DLTs occurring during the first 28 days of treatment with RUXOLITINIB and PANOBINOSTAT will be considered and included in dose escalation decisions. However, all safety information including adverse events, ECG monitoring data, and vital sign abnormalities, will be included in the final decision for dose escalation and determination of how many patients should be evaluated at a given dose level.

Thrombocytopenia will only be considered a DLT in the combination phase (Day 1-28) if the platelet count is recorded below 10,000/ μ l by manual count or $\geq 10,000/\mu\text{l}$ and associated with a grade 3 bleed. Phase I patients who require platelet transfusions within Days 1-28 will have to be removed from study. Patients are allowed to receive platelet transfusions after day 28 if clinically warranted, and this does not necessitate removal from study. Transfusional support of red blood cells (RBC) is permissible at any point in the study and is not considered a DLT.

In the event that an AE begins during the first 28 days of combination therapy, but does not qualify for the definition of a DLT at the time of the dose-escalation decision, due to a specific length requirement until Cycle 2; it will be provisionally considered a DLT during the decision-making process. Adverse events occurring after treatment day 28 will not be considered DLTs, however, they will guide the decision of dose escalation and how many patients will be evaluated at a given dose level. All AE's, vital signs, and ECG data will be included in the final analysis to determine the MTD and/or RPTD.

Table 6-3 Criteria for Defining Dose Limiting Toxicity (DLT)

TOXICITY	Any of the following criteria:
Hematologic	
Febrile Neutropenia	≥Grade 3 (ANC < 1.0 x 10 ⁹ /L + Fever single reading >38.3°C or ≥38°C sustained >1 hr)
Thrombocytopenia	<10 x 10 ⁹ /ul or ≥10 x 10 ⁹ /ul associated with grade 3 bleeding
Non-Hematologic	
Gastrointestinal	
Vomiting	≥Grade 3
Nausea	≥Grade 3 nausea uncontrolled despite use of standard anti-emetics
Diarrhea	≥Grade 3 Diarrhea
Constitutional symptoms	
Fatigue	Grade 4 Fatigue

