Hepatobiliary	
Bilirubin	≥Grade 3, Coincident Direct Bilirubin ≥0.5mg/dl
AST/SGOT and/or ALT/SGPT	≥ Grade 3
	≥Grade 4
Other	
Any Grade 3 non-hematologic toxicity : With the exception of: ≥Grade 3 QTc prolongation (QTc > 500 ms), which is a DLT at any incidence	
Any Grade 4 non-hematologic toxicity	

Any of the following AEs, which when assessed as treatment related, will require patients to be permanently discontinued from study:

- any grade ≥ 3 hemorrhagic event
- 2nd episode of grade ≥ 3 febrile neutropenia
- grade 3 renal toxicity
- grade ≥ 3 QTc prolongation (QTc > 500 ms)
- grade 4 renal toxicity
- grade 4 serum bilirubin with direct bilirubin ≥ 0.5 mg/dL
- grade 4 non-hematologic toxicity

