6.2.7 Dose modification and dose delay

Transfusional support as clinically indicated is also permissible at the discretion of the investigators.

Dose modification rules in Phase I cycles 2-6 (Day 29 - 168) and beyond cycle 7 (Day 169+) or any time in phase II are shown in Table 6.2.3 below. These are to be followed for patients in Phase I as well as Phase II expansion and extension stages. Dose reductions (for PANOBINOSTAT) based on platelet count will be allowed and the dose of PANOBINOSTAT will not go below 5mg PO TIW QOW. See Table 6.2.1/6.2.2 for PANOBINOSTAT and RUXOLITINIB dose levels. The dose of RUXOLITINIB will not be reduced below 5mg PO BID.

Based on the expected occurrence of thrombocytopenia in this patient population with the combination of these agents, we intend to submit a request for agency feedback form to update the safety data in terms of thrombocytopenia after 10 patients have been enrolled on this study. If the safety profile with the combination of PANOBINOSTAT and RUXOLITINIB is acceptable in terms of incidence of platelet count below $20 \times 10^9/L$ and grade 3 or higher bleeding events, then we will continue the study with a threshold of $20 \times 10^9/L$ for dose holding/modification. If there is a single incidence of grade 3 or higher bleeding in association with a platelet count of $<35 \times 10^9/L$, then this threshold will be modified accordingly. This determination will be made after review by the FDA.

Table 6.2.1 RUXOLITINIB dose levels for dose modifications in Cycles 2+ (day 29+)

Dose level	RUXOLITINIB	Comment
-1	5mg PO BID	Lowest dose allowed in the study
0	10mg PO BID	Starting dose in induction phase for all patients on study
1	15mg PO BID	Starting dose for cohort 4a, 4b

Table 6.2.2 PANOBINOSTAT dose levels for dose modifications in Cycles 2+ (day 29+)

Dose level	PANOBINOSTAT	Cumulative dose (per cycle)	Comment
-1	5mg PO TIW QOW	30mg	Lowest allowable dose on the study
0	10mg PO TIW QOW	60mg	Starting dose of cohort 1
1	15mg PO TIW QOW	90mg	Starting dose for cohort 2, 4a
2	20mg PO TIW QOW	120mg	Starting dose for cohort 3, 4b
3	10mg PO TIW QW	120mg	Starting dose for cohort 5
4	15mg PO TIW QW	180mg	Starting dose for cohort 6
5	20mg PO TIW QW	240mg	Maximum dose allowed in study

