Dose modifications or interruptions for adverse events occurring during the DLT-definition period (Cycle 1 Day 1 through Cycle 1 Day 28 of Phase I), and considered as treatment-related will not be allowed. This would require removal of a patient with a DLT within Day 1-28 of Phase I.

Beginning in cycle 2 (day 29), patients who do not tolerate the protocol-specified dosing schedule are permitted to dose adjust in order to allow the patient to continue the study treatment. Tables 6.2.1 and 6.2.2 outline the possible dose level reductions permitted depending on the current dose of each drug at the time of the AE. Patients who experience toxicity at either a dose of RUXOLITINIB at 5mg PO BID or PANOBINOSTAT at 5mg PO TIW QOW cannot be dose reduced further and will be removed from study. Table 6.2.3 and Table 6-4 provide instruction on management per toxicity. All dose modifications should be based on the worst preceding toxicity (CTCAE version 4.0). Patients who require dose hold of RUXOLITINIB are allowed to receive steroids (prednisone, dexamethasone, etc) as per the Investigators discretion to avoid or blunt potential RUXOLITINIB-withdrawal syndrome.

All adverse events should be treated as per the local standard of care and referred to a specialist if clinically indicated. Investigators can use their discretion when making dose-reduction decisions unless otherwise specified in the guidelines below.

If at any time during the study period the use of a strong CYP3A4 inhibitor becomes necessary to treat the patient, a dose modification for RUXOLITINIB is necessary. See Section 6.3 for permitted or prohibited concomitant medications for this study. Also see Section 6.3.4 for dose modification schema for RUXOLITINIB.

Table 6.2.3 Criteria for dose modifications of RUXOLITINIB and PANOBINOSTAT due to study drug-related toxicity from Day 29 and beyond in Phase I or anytime in Phase II (see Table 6-6 for QT prolongation dose management)

Worst Toxicity CTCAE Grade* unless otherwise specified (Value)	Dose Modification Guidelines At any time during a cycle of therapy (including intended day of dosing)	
HEMATOLOGICAL TOXICITIES		
Thrombocytopenia	< 20 x 10 ⁹ /L	Interrupt study treatment dosing until resolved to ≥ 20 x 10 ⁹ /L, then restart study treatment at reduced level as per Table 6.2.1/6.2.2.

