	> 20 x 10 ⁹ /L + grade 3 bleed	Interrupt study treatment dosing until bleeding is resolved and platelet count is at level before bleed was noted, then resume study treatment at reduced level as per Table 6.2.1/6.2.2
Neutropenia (ANC)	Grade 4 (ANC < 0.5 x 10 ⁹ /L)	Interrupt study treatment dosing until resolved to ≤ grade 2, or baseline, then: 
 • If resolved within 7 days restart study treatment at an unchanged dose level • If resolved in more than 7 days then restart study treatment at reduced level as per Table 6.2.1/6.2.2
	Febrile neutropenia (ANC < 1.0 x 10 ⁹ /L, fever ≥ 38.5°C)	Interrupt study treatment dosing until fever resolved and ANC ≤ grade 2, then restart study treatment at reduced level as per Table 6.2.1/6.2.2
Anemia[#] only requires dose reductions after cycle 6 (day 169+)	Doubling of transfusion frequency from baseline or hemoglobin 2g/dL below baseline (screening period)	Hold PANOBINOSTAT only and continue RUXOLITINIB, if hemoglobin (or transfusion frequency) returns to baseline within 28 days restart PANOBINOSTAT at same dose, if this recurs again then reduce dose as per TABLE 6.2.1/6.2.2
NON-HEMATOLOGICAL TOXICITIES		
CARDIAC		
Cardiac - Prolonged QT interval**	Please refer to Table 6-6, Section 6.2.8 and Section 7.2.7.	

Worst Toxicity CTCAE Grade* unless otherwise specified (Value)		Dose Modification Guidelines At any time during a cycle of therapy (including intended day of dosing)
GASTROINTESTINAL		
Diarrhea	Grade 2 (4-6 stools/day over baseline, etc) despite the use of optimal anti-diarrheal medications	Hold PANOBINOSTAT dosing until resolved to \leq grade 1, or baseline, then restart at unchanged dose level
	Grade 3 (\geq 7 stools/day over baseline, etc) despite the use of optimal antidiarrheal medications	Hold PANOBINOSTAT dosing until resolved to \leq grade 1, or baseline, then restart study treatment at reduced level as per Table 6.2.2
	Grade 4 (life-threatening consequences, hemodynamic collapse, etc) despite the use of optimal antidiarrheal medications	Permanently discontinue study treatment dosing
Vomiting/Nausea***	Grade 1 & 2 not requiring treatment or controlled using standard anti-emetics	Maintain dose level
	Grade 3 or 4 vomiting or Grade 3 nausea that cannot be controlled despite the use of standard anti-emetics	Interrupt study treatment dosing until resolved to \leq grade 1, or baseline, then restart study treatment at reduced level as per Table 6.2.1/6.2.2
Fatigue		

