8.1 Adverse events

8.1.1 Definitions and reporting

An adverse event is defined as the appearance of (or worsening of any pre-existing) undesirable sign(s), symptom(s), or medical condition(s) that occurs after patient's signed informed consent has been obtained. Abnormal laboratory values or test results occurring after informed consent constitute adverse events only if they induce clinical signs or symptoms, are considered clinically significant, require therapy (e.g., hematologic abnormality that requires transfusion or hematological stem cell support), or require changes in study medication(s).

Adverse events that begin or worsen after informed consent should be recorded in the Adverse Events eCRF. Conditions that were already present at the time of informed consent should be recorded in the Medical History eCRF. Adverse event monitoring should be continued for at least 30 days following the last dose of study treatment. Adverse events (including lab abnormalities that constitute AEs) should be described using a diagnosis whenever possible, rather than individual underlying signs and symptoms. When a clear diagnosis cannot be identified, each sign or symptom should be reported as a separate Adverse Event.

Adverse events will be assessed according to the Common Terminology Criteria for Adverse Events (CTCAE) version 4.03. If CTCAE grading does not exist for an adverse event, the severity of mild, moderate, severe, and life-threatening, corresponding to Grades 1 - 4, will be used. CTCAE Grade 5 (death) will not be used in this study; rather, information about deaths will be collected through a Death form.

The occurrence of adverse events should be sought by non-directive questioning of the patient (subject) during the screening process after signing informed consent and at each visit during the study. Adverse events also may be detected when they are volunteered by the patient (subject) during the screening process or between visits, or through physical examination, laboratory test, or other assessments. As far as possible, each adverse event should be evaluated to determine:

1. The severity grade (CTCAE Grade 1-4)
2. Its duration (Start and end dates)
3. Its relationship to the study treatment (Reasonable possibility that AE is related: No, Yes) or

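### Table 6.2.3 forces a febrile neutropenia hold only from 38.5°C, above the protocol's own Grade 3 fever cut-off, so a narrow band of first Grade 3 episodes has no required dose action

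*Combined protocol and SAP*

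**What the plan says.** Section 6.2.7 states that the dose-modification rules for Phase I after the first combination cycle "or any time in phase II are shown in Table 6.2.3 below". Four parts of the protocol bear on febrile neutropenia.

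- **Table 6.2.3, febrile neutropenia row.** The trigger is "Febrile neutropenia (ANC < 1.0 x 10 ⁹ /L, fever ≥ 38.5°C". Both drugs are interrupted until the fever has gone and ANC is Grade 2 or better, then restarted one level down. The column heading is "Worst Toxicity CTCAE Grade* unless otherwise specified (Value". The table footnote and the text of section 6.2.7 cite CTCAE 4.0.
- **Table 6.2.3, Grade 4 neutropenia row.** The trigger is ANC <0.5 x 10^9/L. Treatment is interrupted until Grade 2 or baseline. The dose is unchanged if recovery takes 7 days or less and reduced if it takes longer.
- **Table 6-3 (section 6.2.5).** Grade 3 or higher febrile neutropenia is ANC <1.0 x 10^9/L with "Fever single reading >38.3°C or ≥38°C sustained >1 hr". The section adds that "Table 6-3 was created using Common Terminology Criteria for Adverse Events (CTCAE) v4.03", and section 8.1.1 says "Adverse events will be assessed according to the Common Terminology Criteria for Adverse Events (CTCAE) version 4.03".
- **Discontinuation list (section 6.2.5).** Among the treatment-related events that end participation is "2nd episode of grade ≥ 3 febrile neutropenia".

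Beyond the tables, section 6.2.7 says "Investigators can use their discretion when making dose-reduction decisions unless otherwise specified in the guidelines below".

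**The concern.** The two tables describe the same toxicity with the same ANC cut-off but different fevers, and the protocol gives no reason for the higher one in Table 6.2.3. An episode can therefore be Grade 3 by the protocol's own definition and still fall short of the rule meant to manage it.

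Three consequences follow for a patient in that position:

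- Two myelosuppressive drugs may be continued through a first neutropenic fever without a required interruption.
- Section 6.3.2 does not allow G-CSF while study drug is being given, so that support is available only if the investigator chooses to hold.
- The episode, if treatment related, is the first of the two that end participation. The patient can reach the second without the hold and reduction that would normally come between.

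The written rule carries some weight here because the study has no data monitoring committee (section 8.6) and no site monitoring (section 9.1).

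**Working it through.** The plan gives no figure to reproduce. The check compares thresholds and then looks for any other rule that covers the remainder.

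**Step 1. Regions.**
- Grade 3 by Table 6-3: ANC <1.0 and (single reading >38.3°C, or ≥38.0°C for more than 1 hour).
- Mandatory hold and reduction by Table 6.2.3: ANC <1.0 and fever ≥38.5°C.
- Mandatory hold by the Grade 4 row: ANC <0.5 at any temperature.

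**Step 2. Remainder: the first region minus the other two.**
- ANC: 0.5 to <1.0 x 10^9/L.
- Single reading: >38.3 to <38.5°C, width 38.5 − 38.3 = 0.2°C.
- Sustained fever: 38.0 to <38.5°C, width 38.5 − 38.0 = 0.5°C.
- Assuming a thermometer that reads to 0.1°C, this is one single-reading value (38.4) and five sustained values (38.0, 38.1, 38.2, 38.3, 38.4).

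**Step 3. Does another rule require a hold or reduction in the remainder?**
- Table heading: the CTCAE grade applies unless a value is given. This row gives one, so the grade alone does not trigger it. For the same reason, the 4.0 versus 4.03 citation does not change the comparison.
- Section 6.2.7.1: covers Grade 3 or 4 non-hematologic events missing from Table 6.2.3. Febrile neutropenia is in the table, under hematologic toxicities. A concurrent unlisted Grade 3 infection would force a hold; an isolated episode would not.
- Section 6.2.7, intolerable Grade 2 events: also non-hematologic, and dependent on judgment of acceptability.
- Section 6.2.5 list: acts on the second episode, not the first.
- Section 6.2.9: after a treatment-related toxicity of Grade 3 or higher other than thrombocytopenia, it bars re-escalation and return to the dose level involved. It orders no hold. At most it prevents a same-dose restart once the investigator has held.
- Investigator discretion: permits a hold but does not require one.

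No rule requires action for a first, isolated episode in the remainder.

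**Step 4. When does the gap apply?** In Phase I Days 1 to 28 the same event is a DLT, unless clearly due to extraneous causes, and section 6.2.7 requires removal. The gap opens on Day 29 in Phase I and exists from the start in Phase II.

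**Step 5. How reachable is the ANC range?** Inclusion criterion 4a allows ANC from 0.75. The range 0.5 to <1.0 has width 0.50, and the part open at enrolment is 1.0 − 0.75 = 0.25, or 0.25/0.50 = 50% of the width. This is a share of an interval, not of patients or events.

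**Step 6. Background rates, for context only.**
- Grade 3/4 neutropenia on ruxolitinib in COMFORT-1 was 7.1% (section 1.3.3): 22 x 0.071 = 1.56 of 22 patients if that rate applied.
- Grade 3-4 febrile neutropenia on panobinostat QOW at 30-80 mg in mixed hematologic malignancies was 27.3% (Table 1-2): 22 x 0.273 = 6.01 of 22.
- Table 1-3, which lists events above 15% in 35 myelofibrosis patients at 40 mg TIW QW, has no row for neutropenia or febrile neutropenia. The maximum dose here is 20 mg.

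Neither rate estimates events in the band, and only some such events would fall in it.

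**The case against.** The strongest defence is that 38.5°C is deliberate. One table defines a DLT; the other forces interruption and reduction of both drugs. Low fever is non-specific in this disease: section 7.2.2.2 lists unexplained fever as a constitutional symptom, and Table 1-2 shows pyrexia in 51.5% on panobinostat QOW with none at Grade 3-4. Stopping ruxolitinib also carries the withdrawal risk described in section 1.3.3. A careful clinician would often hold anyway, since section 6.2.7 calls for local standard of care.

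Part of this stands. A lower trigger does mean more interruptions, and the text only permits continued dosing; it does not recommend it. The claim of deliberate design is weaker. The protocol states no rationale, and for other listed toxicities the dose-modification trigger starts earlier than the DLT trigger: platelets below 20 against below 10 x 10^9/L, fatigue from Grade 3 against Grade 4, and diarrhea from Grade 2 despite optimal antidiarrheals against Grade 3. Febrile neutropenia goes the other way.

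A reader might also infer more than the documents support:

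- That first Grade 3 episodes in general go unmanaged. Any episode reaching 38.5°C is covered, and ANC <0.5 forces a hold.
- That at ANC <0.5 the dose may simply stay unchanged after quick recovery. The Grade 4 row says so, but section 6.2.9 bars return to the dose level of a treatment-related Grade 3 or higher toxicity, and the two provisions sit uneasily together.
- That dose finding is compromised. Days 1 to 28 of Phase I use Table 6-3, not Table 6.2.3.

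**Conclusion.** The inconsistency is real and minor. From Day 29 in Phase I and throughout Phase II, a first treatment-related Grade 3 febrile neutropenia at ANC 0.5 to <1.0 x 10^9/L, with a single reading >38.3 to <38.5°C or 38.0 to <38.5°C sustained for more than an hour, requires neither a hold nor a reduction unless a non-hematologic event brings in section 6.2.7 or 6.2.7.1. It nevertheless counts toward permanent discontinuation.

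This rests on reading the 38.5°C value as overriding the grade, as the column heading directs, and on Table 6-3 as the working Grade 3 definition. How often such events would occur cannot be derived from the documents. DLT assessment, MTD, sample size and the response endpoint do not depend on it. The case for changing it is a small safety gain at low cost.

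**What to change.** Make two edits to the febrile neutropenia row of Table 6.2.3 at the next amendment:

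1. Replace the 38.5°C criterion with the Table 6-3 wording, "Fever single reading >38.3°C or ≥38°C sustained >1 hr", keeping ANC <1.0 x 10^9/L and the reduced-dose restart. The uncovered region is then empty.
2. Let treatment restart once the fever has resolved and ANC is Grade 2 or better, or back to baseline, as the Grade 4 neutropenia row already does. Without this, the first edit extends a stricter restart condition to more patients. If Grade 2 means ANC of at least 1.0 (an assumption; the documents give no value), someone enrolled at 0.75 to <1.0 would have to exceed baseline to restart, and section 6.2.6 discontinues a patient whose dose is delayed by more than 90 days.

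No visits, tests or patients are added. The cost is slightly more interruptions of both drugs, including ruxolitinib with its withdrawal risk, for which section 6.2.7 allows steroids. There would also be slightly more reductions, and patients already at the lowest dose of either drug would be removed under section 6.2.7.

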6.2.7.1 Dose modifications for Grade 3 or 4 non-hematologic toxicity

Patients experiencing new (or treatment emergent) CTCAE grade 3 or 4 non-hematologic AEs not listed in Table 6.2.3, should have their treatment temporarily discontinued until the adverse event resolves to \leq CTCAE grade 1 or baseline. If the AE was considered related to study treatment, the drug should then be restarted at reduced level according to Table 6.2.1/2.2. If the AE was considered not related to study treatment, then therapy may be restarted (when the AE resolves to \leq grade 1 or baseline) at the current dose.

6.2.8 Dose modifications for prolonged QTc interval

All cardiac events should be treated as per the local standard of care and referred to a specialist if clinically indicated. Any final decision concerning dose modifications or permanent discontinuation of the patient from study drug due to QTc prolongation will be based on the assessment of the Investigator. If a patient cannot be dosed due to prolonged QTc for more than 7 days since last dose, the patient should be discontinued from study. See Table 6-4 for further details on criteria for dose delays, dose reductions, and re-initiation of study treatment for drug related QTc abnormalities.

Table 6-4 Criteria for dose delays, dose reductions, and re-initiation of treatment due to study drug related QTc abnormalities*

ECGs to be performed at specified time point	Abnormality Noted	Dose Modification Guideline - At any time during a cycle of therapy (including intended day of dosing)
Pre-Dose Combination phase day 1 (triplicate ECGs only)		
Pre-dose in cycle 1, Day 1 : 3 ECGs separated by 5-10 minutes, obtained prior to dosing	One of the three ECGs obtained shows QTc > 500 msec	Check and correct the patient's serum potassium, magnesium and calcium immediately, as well as evaluate con-meds.. Delay PANOBINOSTAT dose at least 3 days and repeat ECGs in triplicate. If the 3 ECGs: QTc > 500 msec, discontinue patient from study.
Post-Dose Combination phase day 1 and Subsequent Cycles (triplicate ECG only)		
3 hr Post-Dose: triplicate ECGs Cycle 1, Day 1, 5, 8, 15, 22 Cycle 2 Day 1 (Day 29) and beyond	One of the three ECGs obtained shows QTc > 500 msec OR QTc increased > 60 msec compared to baseline.	Check and correct the patient's serum potassium, magnesium and calcium immediately, as well as evaluate con-meds. Monitor ECG hourly or by telemetry until at least 2 consecutive hourly ECGs performed at least 3 hours post dose are <500. If any ECG has QTc > 500 msec. discontinue patient from study.

* If there are no additional procedures to be carried out on the day, arrangements may be made such that the ECGs may be performed at their local physician's office near the patient's home and transmitted to the site investigator or responsible delegate in a timely manner. ECGs done outside the MSSM MPD clinic are only permitted day 29 and beyond.

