7.2.7 Cardiac assessments

7.2.7.1 Electrocardiogram (ECG)

12-Lead ECG evaluation will be performed per Table 7-1 and Appendix 2. For phase I patients only, cycle 1 day 1 ECG tracings will be done in triplicates to obtain the mean, and should be separated by 5-10 minutes each. On treatment days when ECGs are to be performed, the patient should take their study medication in the clinic.

The mean of the 3 ECGs obtained pre-dose on cycle 1 day 1 will be calculated by the Investigators and will be used as the baseline value to compare to throughout the study. If a prolonged QTc interval is noted at any time, additional days of QTc monitoring may be required (see Table 6.4).

Treatment decisions should be based on the real-time assessment of QTc values at the clinical center, as determined by the automated machine reading or as measured and calculated by trained personnel at the site. All cardiac events should be treated as per the local standard of care and referred to a specialist, if clinically indicated (see Section 6.2.8 for required dose modifications for prolonged QTc). Any final decisions concerning dose modifications or permanently discontinuing the patient from study drug due to QTc prolongation will be based on the assessment performed by the Investigator.

Table 7-1 12-Lead ECG schedule time points:

Screen/Cycle	DAY	Pre-dose	Post dose
		0-hour	3-hour
Screening	Baseline	x	
Cycle 1	1	x	x
	4, 8, 15, 22	x	
Cycle 2	1, 8, 15, 22	x	
Cycle 3+subsequent cycles	1, 15	x	
Cycle 6	29	x	
Cycle 6-12	1	x	
Cycle 12+	1*		

- After cycle 12 ECG is no longer required prior to dosing and can be performed at any time during the visit

ECGs will be performed at the scheduled time points, at a minimum, as indicated above as well as in Appendix 2. If there are no additional procedures to be carried out on that day, arrangements may be made such that the ECGs may be performed at a local office of a

physician near the patient's home and transmitted to the site investigator or responsible delegate in a timely manner. ECGs should be performed on the day of dose administration and, therefore, should there be a delay in dose administration, the corresponding pre-and/or post-dose ECGs should be delayed accordingly.

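### Table 6-4 acts on post-dose triplicate ECGs that Table 7-1 mostly does not schedule, and the QTc baseline for added Phase II patients is stated inconsistently

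*Combined protocol and SAP*

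**What the plan says.** - **Section 6.2.8, Table 6-4.** The pre-dose row calls for three tracings before dosing on Cycle 1 Day 1. The post-dose row covers "3 hr Post-Dose: triplicate ECGs Cycle 1, Day 1, 5, 8, 15, 22" and then "Cycle 2 Day 1 (Day 29) and beyond". It is triggered when "One of the three ECGs obtained shows QTc > 500 msec" or "QTc increased > 60 msec compared to baseline". Neither row is limited to one phase. The response to a trigger is electrolyte correction, review of other drugs and repeated ECGs; leaving the study follows from a tracing above 500 msec.
- **Section 7.2.7.1, Table 7-1** ("12-Lead ECG schedule time points"). The 3-hour post-dose column has one mark, on Cycle 1 Day 1. The remaining Cycle 1 days are 4, 8, 15 and 22, all pre-dose. Later cycles carry pre-dose marks, and the row for Cycle 12 onward has no timed mark.
- **Section 7.2.7.1, text.** "For phase I patients only, cycle 1 day 1 ECG tracings will be done in triplicates to obtain the mean". The mean of the three pre-dose tracings is the reference value for the whole study. Also, "ECGs should be performed on the day of dose administration". The schedule is described as a minimum, and monitoring days may be added once prolongation has been noted.
- **Section 6.2.5, Table 6-3.** "Grade 3 QTc prolongation (QTc > 500 ms), which is a DLT at any incidence". Only DLTs in the first 28 days of combination treatment count for escalation. The list below the table makes treatment-related QTc above 500 ms a reason for permanent discontinuation.
- **Sections 4.1 and 10.4.2.2.** Phase II adds 16 patients to 6 from Phase I, 22 in all.

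**The concern.** A rule can act only on measurements that are taken. A site that follows Table 7-1 to the letter complies with Section 7.2.7.1, yet never obtains most of the tracings that the post-dose row of Table 6-4 presupposes.

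Two things depend on this. The first is the DLT count, in cohorts of 3 to 6 patients. Under Section 10.4.2.1, one missed DLT turns 1 of 3 (add three patients) into 0 of 3 (escalate), or 2 of 6 (MTD exceeded) into 1 of 6 (escalate). The second is the change-from-baseline rule. It needs one agreed reference value, and a single tracing is a noisier reference than a mean of three.

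Timing matters because Table 1-4 attributes QT prolongation to panobinostat, while Section 1.3.3.1 reports a negative thorough QT study for ruxolitinib. Section 1.2.4 puts the median time to peak panobinostat level within 2 hours of dosing.

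**Working it through.** The plan states no figure to reproduce here. The check sets the passages side by side and adds one simple exposure calculation.

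**1. Cycle 1 time points**

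| Day | Table 6-4, 3 h post-dose | Table 7-1, 3 h post-dose | Table 7-1, pre-dose |
|---|---|---|---|
| 1 | yes | yes | yes |
| 4 | no | no | yes |
| 5 | yes | no | no |
| 8 | yes | no | yes |
| 15 | yes | no | yes |
| 22 | yes | no | yes |

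Table 6-4 has 5 post-dose time points, or 5 × 3 = 15 tracings. Table 7-1 schedules 1 of the 5. Days 5, 8, 15 and 22 have no post-dose ECG, and Day 5 has no ECG at all. From Cycle 2 on, Table 7-1 schedules no post-dose ECG.

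**2. Agreement with dosing days.** Section 6.1.1 gives Days 1, 3 and 5 as an example of the three weekly doses, and the Appendix 5 diaries print that pattern, with Day 4 as ruxolitinib only. Assume every-other-week dosing falls in weeks 1 and 3, the first dose being on Day 1. Panobinostat days are then 1, 3, 5, 15, 17 and 19, so Days 8 and 22 are not panobinostat days. Of Table 6-4's five days, three (1, 5, 15) follow a panobinostat dose, and two of those three (5, 15) are unscheduled in Table 7-1. This applies to cohorts 1, 2, 3, 4a and 4b, five of the eight in Table 6-2. In the weekly cohorts (5 to 7) all five days are panobinostat days and four are unscheduled.

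**3. How far the later scheduled ECGs are from a dose.** Fraction of the last dose remaining = 2^(−t/h), with h = 15 to 18 hours (Section 1.2.4) and earlier doses ignored:
- Day 4, t = 24 h: 2^(−24/15) = 33% to 2^(−24/18) = 40%.
- Days 8, 15 and 22 on weekly dosing, and Days 8 and 22 on every-other-week dosing, t = 72 h: 2^(−72/15) = 3.6% to 2^(−72/18) = 6.3%.
- Day 15 on every-other-week dosing, t = 240 h: about 0.01% or less.

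These are plasma fractions. The documents do not give the time course of the QTc effect.

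**4. What remains in the DLT window.** A Phase I patient has 2 occasions on Day 1 and 1 on each of Days 4, 8, 15 and 22: 2 + 4 = 6. Table 6-3 sets no post-dose or triplicate condition, so QTc above 500 ms on any of the six is a DLT.

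**5. Baseline in Phase II.** Section 7.2.7.1 needs three pre-dose Day 1 tracings for the reference value but restricts Day 1 triplicates to Phase I. The pre-dose row of Table 6-4 asks for three tracings without a phase limit. Table 7-1 marks a Day 1 pre-dose ECG for everyone without giving a number. The conflict concerns the 16 added patients, 16/22 = 73% of the Phase II set.

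**The case against.** The strongest reply is that the tables can be read cumulatively. Table 7-1 is a minimum, and the first column of Table 6-4 is itself worded as a list of ECGs to be done. That reading is possible, but nothing says which table governs, and a site doing only the minimum is compliant. The provision for added monitoring starts once prolongation has been seen, so it cannot recover what was not looked for.

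Other points on that side carry weight:
- Ruxolitinib is taken daily, so Day 4 is a study-drug day. Appendix 2 allows visits to move by 3 days, which can absorb Day 4 versus Day 5. The day mismatch is therefore minor; the mismatch between pre-dose and post-dose is not resolved by a visit window.
- Section 1.2.4 gives a Day 5 accumulation ratio of about 1.14, so the Day 1 post-dose ECG is taken at exposure not far from that on Day 5.
- Section 1.2.3.1 reports QTc above 480 msec mostly at 60 mg three times weekly every week, while the highest planned dose here is 20 mg on that schedule. Missed events may be few.
- A rise above 60 msec is not listed as a DLT, and Table 6-4 does not by itself make it a reason for removal.

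A reader might infer that QTc DLTs cannot be ascertained at all, or that Phase II patients have no baseline ECG. The documents support neither: six ECG occasions can reveal a DLT, and a Day 1 pre-dose ECG is scheduled in both phases. Nor can Appendix 2 be used to confirm Table 7-1. Its Phase 2 visit header shows Day 4, but its ECG row cannot be read in the available text.

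**Conclusion.** The inconsistency is real and bears on a safety rule and on the dose-finding endpoint. Four of five Cycle 1 post-dose time points in Table 6-4, and all from Cycle 2 on, are absent from Table 7-1. For every-other-week cohorts the count is two of three panobinostat days, if dosing is in weeks 1 and 3. The consequence is incomplete post-dose ascertainment after Day 1, with possible under-detection of QTc DLTs; the documents give no basis for estimating how many. Separately, the 60 msec rule has conflicting baseline definitions, single or triplicate, for the 16 added Phase II patients. The 73% counts patients affected by that ambiguity and is not a measure of harm.

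The reading of Table 7-1 relies on its column positions in the extracted text. The table's note that ECGs need not precede dosing after Cycle 12 supports reading the earlier marks as pre-dose.

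**What to change.** Reconcile Table 6-4, Table 7-1, the text of Section 7.2.7.1 and Appendix 2 so that:
- every ECG on which a rule acts appears in the schedule, with its timing relative to dosing and its number of tracings;
- ECG days agree with dosing days, separately for the every-other-week and weekly cohorts;
- one QTc baseline definition covers Phase I and Phase II.

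Correct at the same time the references in Table 6.2.3 to a Table 6-6, which is not in the list of tables. Which ECG schedule applies is the sponsor's clinical decision, and none is proposed here. The cost is amendment wording and, depending on the choice, a changed number of ECGs.
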